14.0 Withdrawal of Subjects*

14.1 AmeriSpeak panel members may choose to complete study procedures or not. Reasons for which participants may choose to discontinue participation in the study may include loss of interests or lack of time to complete remaining procedures. There are no foreseeable circumstances where the investigators or research team will withdrawal participants without their consent; we will not have the ability to directly communicate with participants since all participants are anonymous to the research team.

PROTOCOL TITLE: Randomized Trial Testing the Efficacy of Hookah Tobacco Public Education Messages among Young Adults

14.2 Participants who voluntarily withdraw from the study will choose to on their own. There are no procedures for termination.

14.3 The only manner in which participants will withdrawal is if they decide to on their own. There will be no partial withdrawal with continued data collection in this study.

15.0 Risks to Subjects*

15.1 This study does not involve drugs, devices, or medical procedures. The primary potential source of risks in this study is the social risk of gathering behavioral information about tobacco use and tobacco-related attitudes, perceptions, and beliefs. These include potential embarrassment and fear of disclosure of potentially sensitive information, and confidentiality concerns.

16.0 Potential Benefits to Subjects*

16.1 There are no direct benefits to young adults who choose to participate in this research. The knowledge gained from the study will help us to understand how to best design hookah tobacco public education messages to prevent and reduce hookah use among young adults in the future.

17.0 Data Management* and Confidentiality

17.1 We calculated statistical power to test our study hypotheses assuming a two tailed $\alpha = .05$ and baseline sample of 1100 participants, including 425 young adult hookah users and 675 susceptible non-users. We estimated the ability to detect effects of the messages on hookah initiation among susceptible non-users⁴⁴ and cessation among current users²¹ based on prior studies. Among susceptible non-users, we estimate 8% will initiate hookah use over the 6-month follow-up period based on our recent national study of US young adults.⁴⁴ With susceptible non-users at 6-month follow-up we will have 80% power to detect percent differences as small as 5.3%, or initiation of 8% in the control arm and 2.7% in the messaging arm. This equates to an odds ratio of 0.62 comparing hookah initiation between the messaging and control arms in a logistic regression analysis including covariates. Although evidence on hookah tobacco cessation rates is limited, 1 prior study found that young adult hookah users exposed to risk-based messages were nearly 2 times more likely than those in a control condition with no message exposure to report cessation at 6-month follow-up (62% vs. 33%, odds ratio 1.89).²¹ Conservatively assuming a much lower overall cessation rate of approximately 10% (i.e., comparable to those of behavioral smoking cessation interventions)⁵³ the sample of hookah users at the 6-month follow-up will have 80% power to detect absolute differences in cessation between study arms as small as 8% (10% control, 18% messaging). In a logistic regression analytic framework with covariates, this equates to an odds ratio of 1.55. For analyses of continuous outcome variables, our sample will provide 80% power to detect small mean differences ($d \leq 0.10$) between arms in the complete sample, and among susceptible non-users and current users separately. For testing mediating effects,

PROTOCOL TITLE: Randomized Trial Testing the Efficacy of Hookah Tobacco Public Education Messages among Young Adults

simulation studies provide estimated power to detect mediation effects using bias-corrected bootstrap analyses.⁵⁴ The sample will provide 80% power to detect small- to medium- indirect (i.e., coefficients in the range of 0.20-0.30) effects. Similarly, for analyses of the interaction between study condition and two-level moderators we will have 80% power to detect moderator effects as small as Cohen's $f \leq 0.10$ in ANCOVA analyses (i.e., differences between susceptible non-users and hookah users) and odds ratios as small as 1.70 for interactions between non-hookah tobacco use and trial arm for binary initiation and cessation outcomes.

The primary outcomes and analytic approach will compare differences in 6-month outcomes across the control and messaging arms. We will initially assess differences in past 30-day hookah use behavior using longitudinal mixed effects logistic regression in the entire sample. The model will include past 30-day hookah use at 6 months as the dependent variable, trial arm, and baseline covariates for susceptible non-user/current user and any others identified in the steps outlined above.⁵⁵ We will then use a similar modeling strategy to assess differences by trial arm in hookah use initiation among participants who were susceptible non-users at baseline, and cessation among baseline users. These analyses will model dependent variables reflecting change in hookah use status from baseline to the 6-month follow-up separately for these two groups, a term for trial arm, and any covariates as identified above. Among susceptible non-users at baseline, we will similarly analyze changes in susceptibility status relative to trial arms as a secondary outcome. In both susceptible non-users and hookah users, will also conduct analyses to assess message effects on continuous outcome measures at 6 months, curiosity to use hookah tobacco and motivation to quit, respectively. We will use repeated measures ANCOVA to compare means of the continuous outcomes by trial arm at 6 months and Tukey's adjustment method for the pair-wise comparisons. In exploratory analyses, we will repeat these types of mixed logistic and ANCOVA analyses for outcomes measured at the 1- and 3-month time points. We will assess any potential message order effects separately in the education messaging arm by examining message effects by the 4x4 Balanced Latin Square orders. If any message order effects are detected or trends are observed we will include order as a covariate in analyses.⁵⁶ Exploratory analyses will also examine if responses to weekly assessments differ by message themes using approaches similar to those above.

We will test hypotheses about potential mediation of message effects through a series of steps drawing from traditional mediation frameworks for preliminary analyses⁵⁷ and applying more robust methods to formally test for mediation.⁵⁸ First, we will examine differences in means for mediating variables by trial arms and investigate whether each mediator at 1- and 3-month time points is correlated with the outcomes at 6-months using bivariate statistics and regression-based analysis accounting for any covariates as needed. Where these preliminary steps indicate potential mediation, we will formally test for mediation by estimating the indirect effects of candidate mediators at 1- and 3-months on study outcomes at 6-

PROTOCOL TITLE: Randomized Trial Testing the Efficacy of Hookah Tobacco Public Education Messages among Young Adults

months via the study arms using a bias-corrected bootstrapping method with 1,000 resamples to address non-normality of the product of the coefficients estimator.^{54, 58} This bootstrapping approach estimates an indirect (i.e., mediation) effect reflecting the product of the effect of trial arm on the mediator with the effect of the mediator on the outcome, and produces bias-corrected asymmetric 95% confidence intervals (CIs) that correct for non-normality of the distribution of indirect effects.⁵⁸ This method provides higher power and better control over the Type I error rate compared with traditional approaches for testing mediation.^{172,173} Asymmetric 95% CIs for indirect effects that do not include zero will indicate significant mediation effects.¹⁷² We will evaluate hypothesized moderators individually by introducing them one at a time and their corresponding interactions with trial arm into the logistic regression and ANCOVA models. Analyses assessing differential effects of messages among susceptible non-users and hookah users will primarily be ANCOVA based and examine mediators and outcomes measured commonly in these groups. Although the primary moderators of interest are those relating to hookah and other tobacco product use, we will also explore potential moderating effects of participant demographics including sex (male, female) and age (< 25, 25+) and other characteristics in analyses.

17.2 NORC also takes extensive measures to ensure that all panel members' privacy and personal information are treated confidentially and kept secure. All personally identifying records are kept secured in a separate data servers maintained by NORC. NORC never provides any panel members' personally identifying information to a research partner without the explicit and informed consent provided by the sampled members. For this study, all data will be de-identified and anonymous to the investigators and no personal information will be released to the investigators, therefore there will be no way to discern participants' identities from the study data. All NORC survey response data are identified only by an anonymous ID number.

17.3 In addition to the measures put into place by NORC, our research team will take several additional steps to ensure data collected from AmeriSpeak panel members are treated as secure and confidential at GUMC. First, as noted above, all data will be anonymous and will not include personally identifying information. Any data to be transferred from NORC to [name] at GUMC/LCCC will use Georgetown Box. We will use Georgetown Box to transfer data files and documentation to [name] by creating a restricted access link that is password protected and only accessible to authorized NORC personnel. Second, once study data are transferred to GUMC/LCCC all electronic study data files will be securely stored on a GUMC/LCCC network drive. This network space is encrypted and directories are password-protected at the individual user level to ensure electronic data files are treated as secure and confidential. Only the GUMC/LCCC Principal Investigator and authorized study

PROTOCOL TITLE: Randomized Trial Testing the Efficacy of Hookah Tobacco Public Education Messages among Young Adults

personnel will be granted access to the data after appropriate permissions are established.

17.4 All study procedures use well-validated assessments with established psychometric properties. Quality control will be ensured by working with NORC to review online assessments we provide to ensure they function properly in terms of item performance, skip logic, and design. There are no other necessary quality control measures.

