2.0 Objectives*

2.1 The purpose of this study is to examine the efficacy of hookah tobacco public health education messages among young adults between the ages 18 to 30, including young adults who are susceptible non-users of hookah tobacco and current users.

2.2 Hypothesis 1: Messages will decrease hookah initiation among susceptible non-users and increase cessation among hookah users.

Hypothesis 2a: Message effects will be mediated by greater message engagement, message receptivity, and perceived harms of hookah tobacco.

Hypothesis 2b: Message effects will be greater among susceptible non-users versus hookah users and among those who do not use other tobacco products versus those who do.

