4.0 Study Endpoints*

4.1 The primary study endpoints among susceptible non-users are changes in susceptibility to use hookah tobacco, curiosity (i.e., intentions) to use hookah tobacco, and hookah tobacco initiation. The primary end

PROTOCOL TITLE: Randomized Trial Testing the Efficacy of Hookah Tobacco Public Education Messages among Young Adults

points among current hookah users are motivation to quit using hookah tobacco, frequency of hookah use, and cessation.

4.2 Secondary end points include perceived harm & addictiveness of hookah tobacco, perceived risk and worry about harm & addictiveness, and message-related outcomes including message receptivity, emotional response, and content recall. These will be examined as mediators of message effects. There are no safety outcomes in this trial.

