AmeriSpeak panel members who are young adults ages 18 to 30 in the US will be sent a standard email invitation describing the study. Potential participants are identified by randomly selecting households within the panel with a young adult within the study age range, and targeting study invitations based on recent study participation, and other demographic characteristics as needed to ensure a representative sample. This email invitation will introduce study procedures and eligibility criteria, and direct interested panel members to the eligibility screener with items to confirm eligibility. Procedures will ensure potential participants are adults ages 18 and older through two steps: 1) targeting study invitations only to those panel members whose age is within this range; and 2) re-assessing age at eligibility screening and excluding those who provide inconsistent information (i.e., ages differ in self-reported screening compared with panel-based age derived from date of birth). Panel members who are confirmed to meet study eligibility criteria will proceed to the online baseline. AmeriSpeak panel members who do not meet study eligibility criteria will be redirected to a concluding thank-you screen. Similar procedures will be followed when participants are contacted for the brief message exposures and the 2-, 4-, and 6-month follow-up assessments. This approach is guided by similar previous tobacco research studies with young adults, including studies with prospective participation and retention rates of 70% and higher.⁴⁵⁻⁴⁶

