12.0 Local Number of Subjects

12.1 Our sample size is 1100 participants, including 425 young adult hookah users and 675 susceptible non-users. We conducted power analyses as described in Section 17 to determine the target sample size.

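### Section 17.1 claims 80% power for cessation of 10% vs 18%, but 425 users give about 66% even with no dropout, and the odds ratios 1.55 and 0.62 contradict their own percentages

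*Combined protocol and SAP*

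**What the plan says.** Section 17.1 sets a two-tailed alpha of .05 and a baseline sample of 425 current hookah users and 675 susceptible non-users. Sections 6.1 and 6.2 randomise equally to two arms, balanced by use status.

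- **Cessation among users.** The users remaining at 6 months are said to give "80% power to detect absolute differences in cessation between study arms as small as 8% (10% control, 18% messaging"). With covariates in a logistic model, the text adds, "this equates to an odds ratio of 1.55".
- **Initiation among non-users.** The text claims 80% power for 8% in the control arm against 2.7% in the messaging arm. It continues: "This equates to an odds ratio of 0.62 comparing hookah initiation between the messaging and control arms".
- **Background for cessation.** One earlier study is summarised as "62% vs. 33%, odds ratio 1.89".

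Section 12.1 rests the sample size on these figures: "We conducted power analyses as described in Section 17 to determine the target sample size". Section 4.1 lists the primary endpoints for users: "points among current hookah users are motivation to quit using hookah tobacco, frequency of hookah use, and cessation". Hypothesis 1 in section 2.2 reads "Messages will decrease hookah initiation among susceptible non-users and increase cessation among hookah users".

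Section 17.1 gives no 6-month retention rate. The only retention figure is in section 6.2, which refers to earlier "studies with prospective participation and retention rates of 70% and higher".

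**The concern.** Two things can be checked from the page. First, 425 users looks too few for 80% power on an 8-point difference starting from 10%. Second, each odds ratio is presented as equivalent to a pair of percentages, yet both lie much closer to 1 than those percentages imply.

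Cessation is a primary endpoint for users and half of Hypothesis 1. If its true power is well below 80%, a null result could be misread as evidence that the messages do not help users quit. The mismatched odds ratios also leave it unclear which effect the trial was sized to detect, because the percentages and the odds ratios describe effects of very different size.

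**Working it through.** **Inputs.** Two-sided alpha 0.05, so z = 1.960; 80% power, so z = 0.842 (section 17.1). Allocation is 1:1 within each group (sections 6.1 and 6.2). Users: 425/2 = 212.5 per arm. Non-users: 675/2 = 337.5 per arm. Retention of 70% to 100% is an assumed range; its lower end is the figure section 6.2 cites from other studies.

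**Formulas.** Two-proportion z test, with p̄ = (p1 + p2)/2:

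- Power = Φ{ [ |p1 − p2| − 1.960·√(2p̄(1 − p̄)/n) ] / √( [p1(1 − p1) + p2(1 − p2)]/n ) }
- n per arm = [ 1.960·√(2p̄(1 − p̄)) + 0.842·√(p1(1 − p1) + p2(1 − p2)) ]² / (p1 − p2)²
- Odds ratio = [p2/(1 − p2)] / [p1/(1 − p1)]

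**Step 1: the plan's cessation claim, 10% vs 18%.** Here p̄ = 0.14. At n = 212.5 the null term is 1.960·√(2 × 0.14 × 0.86/212.5) = 0.0660 and the alternative standard error is √((0.0900 + 0.1476)/212.5) = 0.0334. Power = Φ((0.0800 − 0.0660)/0.0334) = Φ(0.42) = 66%. The stated 80% is not reproduced.

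The required size is (0.962 + 0.410)²/0.08² = 294.1, so 295 per arm or 590 users analysed.

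| Share of 425 analysed | n per arm | Power |
|---|---|---|
| 100% | 212.5 | 66% |
| 90% | 191.25 | 62% |
| 80% | 170 | 57% |
| 70% | 148.75 | 51% |

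The choice of test does not explain the gap. With all 425 analysed, the unpooled, arcsine, log-odds Wald, continuity-corrected, exact chi-square and Fisher versions all give 61% to 67%. A one-sided test, which the plan does not use, gives 77%.

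**Step 2: detectable difference at 80% power from a 10% control rate.** With all 425 analysed: 10% vs 19.6% (odds ratio 2.2). At 70%: 10% vs 21.8% (odds ratio 2.5).

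**Step 3: the plan's initiation claim, 8% vs 2.7%.** The required size is 281.8 per arm, about 564 in total, and 281.8/337.5 = 83.5%. Power is 87% with all 675 analysed, 80% at about 84%, and 73% at 70%. This claim holds if retention is at least about 84%.

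**Step 4: odds ratios from the stated percentages.**

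- Cessation: (0.18/0.82)/(0.10/0.90) = 0.2195/0.1111 = 1.98, against 1.55 stated.
- Initiation: (0.027/0.973)/(0.08/0.92) = 0.0277/0.0870 = 0.32, against 0.62 stated.

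Read the other way, 1.55 from 10% means 14.7% cessation: 31% power with no dropout, and 771 per arm needed for 80%. And 0.62 from 8% means 5.1% initiation: 33% power with no dropout, and 1,155 per arm needed.

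**Step 5: could covariates account for it?** Adjusting for a prognostic covariate normally moves a conditional odds ratio away from 1; 1.55 and 0.62 lie closer to 1. Adjusted logistic regression was simulated with 212 users per arm, marginal rates held at 10% and 18%, and one standard normal covariate. Its log-odds slope per SD is an assumption:

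| Slope per SD | Conditional odds ratio | Power, no dropout |
|---|---|---|
| 0.5 | 2.02 | 68% |
| 1.0 | 2.15 | 71% |
| 1.5 | 2.38 | 77% |

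**Step 6: could 10% be the average over both arms?** That reading gives 6% vs 14%: odds ratio (0.14/0.86)/(0.06/0.94) = 2.55, with 79% power at no dropout and 63% at 70%. It conflicts with the explicit 10% for the control arm, and its odds ratio is even farther from 1.55.

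**Side check.** For the cited study, 62% vs 33% gives an odds ratio of (0.62/0.38)/(0.33/0.67) = 3.31 and a risk ratio of 0.62/0.33 = 1.88. The quoted 1.89 looks like a risk ratio.

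**The case against.** The best defence is that the planned analysis adjusts for covariates, so an unadjusted test understates its power. This has some force. With a covariate slope of 2.0 per SD, simulated power does pass 80%, at about 82% to 83% with no dropout. But that is a very strong predictor, the documents give no such value, and at 70% retention power is still only about 67% to 68%. Adjustment also cannot produce the stated odds ratios, since it moves them the other way. What stands is that replacement figures should be labelled unadjusted.

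A second defence is that 10% vs 18% was chosen as a conservative scenario. At the earlier study's rates, 33% vs 62%, power exceeds 99% even with 70% of users analysed. That is true, but section 17.1 attaches its 80% claim to 10% vs 18%.

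Third, the error biases no estimate and leaves the type I error unchanged. That is also true; what is wrong is the stated basis for the sample size.

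Finally, the missing retention rate is a reporting gap, and the 1.89 is background that does not enter the 10% vs 18% calculation. Both are secondary points. A retention of 84% is compatible with section 6.2, so the initiation power claim is not contradicted.

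**Conclusion.** The concern holds. On the plan's own inputs, power for 10% vs 18% cessation is about 66% at best, not 80%, and about 51% if 70% of users are analysed. The chance of missing the stated effect is therefore at least 34% unadjusted (100% − 66%), rather than 20%. The odds ratios 1.55 and 0.62 are wrong for their percentages at any sample size or retention; the correct values are 1.98 and 0.32.

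The power figures assume 1:1 allocation, two-sided 0.05 and an unadjusted comparison. Only an undocumented, very strong covariate combined with complete follow-up would bring cessation power to 80%. The initiation power statement is sound apart from its odds ratio, given retention of at least about 84%. The whole-sample analysis of past 30-day use is not affected by this point.

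**What to change.** With enrolment unchanged, replace the binary power sentences in section 17.1 with one consistent set, labelled as unadjusted:

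- *Susceptible non-users:* 8% vs 2.7% (odds ratio 0.32) has 87% power if all 675 are analysed, 80% if about 564 (84%) are, and 73% if 70% are.
- *Hookah users:* 10% vs 18% (odds ratio 1.98) has 66% power if all 425 are analysed and 51% if 70% are. The difference detectable with 80% power is 10% vs 19.6% (odds ratio 2.2) and 10% vs 21.8% (odds ratio 2.5), respectively.

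Delete 0.62 and 1.55. State the 6-month retention assumed for each group; if it differs from 70%, replace the illustrative figures accordingly. If a gain from covariates is to be claimed, give the covariate strength assumed. If 10% was meant as the average over both arms, say so and give 6% vs 14% with its odds ratio of 2.55 and power of 79% with no dropout and 63% at 70%. Check the quoted 1.89 against its source and name the measure correctly.

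The cost is protocol wording only. Enrolment, procedures and analyses stay as they are, but the stated cessation power becomes less favourable.

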1.0 Study Summary

Study Title	Randomized Trial Testing the Efficacy of Hookah Tobacco Public Education Messages among Young Adults
Study Design	Two-group randomized trial study design to test message effects prospectively on young adults who are susceptible non-users of hookah tobacco and current users.
Primary Objective	To examine the efficacy of public education messages that target young adults' beliefs about hookah tobacco use in 4 domains: health harms, addiction, social use, and flavoring for preventing and reducing hookah tobacco use.
Secondary Objective(s)	NA
Research Intervention(s)/ Investigational Agent(s)	Education messages about the health harms, addictiveness, social use, and flavoring of hookah tobacco use.
IND/IDE #	NA
Study Population	Young adults between the ages 18 to 30, including young adults who are susceptible non-users of hookah tobacco and current users.
Sample Size	n = 1100 participants
Study Duration for individual participants	Approximately seven (7) months.
Study Specific Abbreviations/ Definitions	NA

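### Frequency of use is a primary endpoint in current users but has no specified analysis; the behavioural models planned for users credit only a move to zero use

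*Combined protocol and SAP*

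**What the plan says.** The primary objective in Section 1.0 covers messages on four themes, ending with "flavoring for preventing and reducing hookah tobacco use". Section 4.1 lists the primary endpoints by stratum; for users, the end "points among current hookah users are motivation to quit using hookah tobacco, frequency of hookah use, and cessation". Frequency and cessation are thus separate primary endpoints. Hypothesis 1 in Section 2.2 is narrower: "Messages will decrease hookah initiation among susceptible non-users and increase cessation among hookah users".

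Section 17.1 sets out the 6-month analysis:

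- Whole sample: "We will initially assess differences in past 30-day hookah use behavior using longitudinal mixed effects logistic regression in the entire sample".
- By stratum, with a similar modelling strategy: "hookah use initiation among participants who were susceptible non-users at baseline, and cessation among baseline users". On the form of the outcome: "These analyses will model dependent variables reflecting change in hookah use status from baseline to the 6-month follow-up".
- Continuous outcomes, by repeated measures ANCOVA: "continuous outcome measures at 6 months, curiosity to use hookah tobacco and motivation to quit, respectively".

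The exploratory analyses repeat the same model types at earlier time points. The moderator analyses use ANCOVA on outcomes shared by users and non-users, without naming them. The power statement covers initiation, cessation, unnamed continuous outcomes, mediation and moderation. None of these names frequency of use.

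**The concern.** Section 10.2 defines a current user by use at least once in the past month, so every user starts at yes on the past 30-day scale. The only change that the scale can record is to no. A user who falls from many sessions a month to one is scored the same as a user who did not change. Cessation, defined as a change of status, has the same property. Motivation to quit is continuous but is not behaviour, so it does not fill the gap.

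At stake is half of the stated aim in users. The plan says that it will learn whether messages reduce use, and it declares the endpoint that would show this, but it specifies no comparison of that endpoint between arms. An analysis of frequency added later would not be prespecified, although it concerns a declared primary endpoint.

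**Working it through.** **1. The plan's own figure.** Section 17.1 states 80% power for cessation of 10% versus 18%, two-sided alpha 0.05, with 425 users at baseline. With pooled variance and equal arms, n per arm = [1.96·√(2·0.14·0.86) + 0.8416·√(0.10·0.90 + 0.18·0.82)]² / 0.08² = (0.9618 + 0.4102)² / 0.0064, which rounds up to 295, or 590 in all. With all 425 users (212.5 per arm), z = (0.08·√212.5 − 0.9618) / 0.4874 = 0.42, so power is 66%. At 70% retention (the level that Section 6.2 cites from earlier studies; 148.75 per arm) it is 51%. The stated 80% is not reproduced. The unadjusted odds ratio is (0.18/0.82)/(0.10/0.90) = 1.98; the plan gives 1.55. The main point does not depend on this, but the yes/no test in users is weaker than stated.

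**2. What a frequency analysis would add.** The documents give no distribution of frequency, so these inputs are assumptions:

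- Zero use at 6 months in control: 10% (the plan's planning rate) or 33% (the control rate in the one earlier hookah study cited in Section 17.1).
- Four ordered use levels among the rest. With 10% at zero, the five levels are 10/60/15/10/5, 10/40/25/15/10, 10/25/30/20/15, 10/22.5/22.5/22.5/22.5 and, for very light use, 10/75/10/4/1. With 33% at zero, the use levels keep the same proportions.
- Effects: a common odds ratio over the whole scale; reduction only (odds ratio 1.98 among continuing users, equal quitting); quitting only. Under the common odds ratio of 1.98, zero use moves from 10% to 18%, or from 33% to about 49% (0.33/0.67 × 1.98 = 0.975; 0.975/1.975 = 0.49).

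The tests are a two-proportion z test on zero versus any use, and a tie-corrected Wilcoxon test (the score test of the proportional-odds model) on the five levels. Power is simulated and good to about one percentage point. Type I error was about 5% for both.

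| Control at zero | Effect | Per arm | Yes/no | Ordinal |
|---|---|---|---|---|
| 10% | common OR 1.98 | 212 | 67% | 87-98% |
| 10% | common OR 1.98 | 149 | 51% | 83-91%* |
| 33% | common OR 1.98 | 212 | 93% | 95-97% |
| 33% | common OR 1.98 | 149 | 82-83% | 88-90%* |
| 10% | common OR 1.6 | 212 | 35-36% | 68-78%* |
| 33% | common OR 1.6 | 212 | 65-66% | 74-76%* |
| 10% | reduction only | 212 | 5% | 32-87% |
| 33% | reduction only | 212 | 5% | 11-41% |
| 10% | quitting only | 212 | 66-67% | 8-36%* |

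*First four shapes only.

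The low ends of the reduction-only rows come from the very light shape. A lighter one still (10/80/7/2/1) gives about 20% with 10% at zero.

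**3. A second model.** Days of use were simulated as zero-truncated negative binomial, capped at 30, with 10% quitting in both arms and continuing control users averaging roughly 4.5-7 days. The messages lower the underlying mean in continuing users by 30% or 50%. With 212 per arm, the yes/no test rejects in about 4-7% of runs. A rank test on days has power of 57-89% (30% reduction) and 97-100% (50% reduction). With 149 per arm, the rank test has 40-76% and 91-100%. These figures are also conditional on 10% zero use.

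**The case against.** The yes/no models match Hypothesis 1, which for users names cessation only, and cessation is a behavioural target in its own right, not an arbitrary cut. That stands, and it is a reason to keep the cessation model. It does not explain why a separate primary endpoint has no analysis.

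The whole-sample model also covers 675 never-users, for whom any versus none is the natural scale. That stands too: the pooled model should not be replaced.

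A reader might infer from the 10% rows that the yes/no scale throws away most of the power. The figures do not support this. Under a common odds ratio of 1.98 the yes/no test keeps well over half of the ordinal power, and with 33% zero use the gap is only about 2-4 points. The 10% rate is one that Section 17.1 itself calls conservative. With 33% zero use or very light use, the ordinal model would itself often miss a reduction, because users already at the lowest level can move only to zero.

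A reader might also infer that a reduction could never be detected, or would be reported as no effect. The documents do not support that either. Frequency is a declared endpoint, so the data should exist and could be analysed, though not as a prespecified comparison. The measures are in an attachment outside the public text, so the response scale of the frequency item is unknown.

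**Conclusion.** The gap is clear from the text alone: a primary endpoint in users, tied to the objective of reducing use, has no specified between-arm analysis, and the behavioural models that are specified respond only to complete stopping. If the messages reduce use without more quitting, those models reject at about 5%, whatever the distribution of use.

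How much a frequency analysis would gain is uncertain. It ranges from a few points to about 30 under a whole-scale odds ratio of 1.98 with 212 per arm. For reduction only, it ranges from a few points above the false-positive rate to more than 80. It depends mainly on the zero-use rate and on how light the use is, neither of which can be settled from the documents. If the messages work only through quitting, the frequency model is the weaker of the two. The case for adding it is that it answers a question the plan poses, not that it is always more powerful. This should be corrected before the analysis.

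**What to change.** In Section 17.1, keep the pooled past 30-day logistic model and the cessation model as they are. Add a prespecified between-arm analysis of 6-month past 30-day frequency in baseline users, with terms for trial arm and baseline frequency. Use a proportional-odds model on ordered frequency with zero as the lowest level, or a count model if the item collected is a count. Report it beside cessation, so that reduced use and quitting are separate conclusions, and state its place among the primary endpoints.

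Restate power for it. The plan's claim of 80% power at d of 0.10 or less in users alone cannot be carried over. For a normally distributed outcome the detectable difference is 2.80 × √(2/212.5) = 0.27 with all 425 users, and 0.33 at 70% retention.

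The cost is wording and one more model. No new data should be needed if frequency is collected as Section 4.1 implies, but the questionnaire must be checked for the item's scale and recall period. The downsides are one more test to place in the order of endpoints, and lower power than cessation if the messages act only through quitting.
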